### **5.2.3 Prohibited medications**

To the degree possible, NSAIDs should be avoided due to their effect on coagulation.

## **5.3 Test and control product**

The test and control products are dissolved in a buffered isotonic saline and have indistinguishable appearances. EXT608 injectable solution is stored frozen (-20°C) and thawed when ready to use. Thawing should take place at room temperature (~25°C), but no higher than body temperature (~37°C), protected from light if possible. It is supplied as a clear solution in a ready-to-use concentration, single use, glass vial at a concentration of 0.4 mg/mL (pH 4.8-6.2). The vehicle/placebo solution consists of sterile saline.

EXT608 is provided as a single dose, glass vial containing a sterile, clear injectable solution in one strength of 0.4 mg/mL.

### **5.3.1 General principles**

Storage is frozen at -20 °C or less.

### **5.3.2 Test treatment**

EXT608 dissolved in a buffered isotonic saline solution.

### **5.3.3 Control treatment**

Buffered isotonic saline solution.

### **5.3.4 Drug Accountability**

Accountability for the study drug at the CRU is the responsibility of the Investigator. The investigator will ensure that the study drug is used only in accordance with this protocol. Where allowed, the Investigator may choose to assign some of the drug accountability responsibilities to a pharmacist or other appropriate individual. Drug accountability records indicating the drug's delivery date to the CRU, inventory at the CRU, use by each subject, and return to the Sponsor (or destruction, if approved by the Sponsor) will be maintained by the CRU. These records will adequately document that the subjects were provided the doses as specified in the protocol and should reconcile all study drug received from the Sponsor or its designee. Accountability records will include dates, quantities, batch/serial numbers, and subject identification numbers. The site monitor will review drug accountability at the site on an ongoing basis during monitoring visits.

### **5.3.5 Disposal, Return or Retention of Study Drug**

All unused and used study drug will be retained at the CRU until inventoried by the site monitor. All used, unused or expired study drug will be returned to the Sponsor or if authorized, disposed of at the study site in accordance with governing regulations and documented.

## 5.4 Blinding

### 5.4.1 Treatment blinding

Two Unblinded pharmacy staff members including at least one pharmacist trained to prepare sterile injectables will prepare the doses. The pharmacy staff can have no other role in the study. The doses will be administered by qualified staff trained to administer subcutaneous injections.

With the exception of the DMB members, all other parties remain blinded to the treatment results, until periodic reviews are performed by the DMB.

### 5.4.2 Endpoint blinding

For safety reasons, no outcomes are blinded.

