### 2.2 Secondary Objectives

The secondary objectives are to assess:

1. Single dose PK including  $AUC_{0-24h}$ ,  $AUC_{0-48h}$ ,  $AUC_{0-28d}$ ,  $AUC_{0-\infty}$ ,  $C_{max}$ ,  $T_{max}$ ,  $T_{1/2}$ ,  $\lambda_z$ ,  $Cl/F$  and  $V_z/F$ .
2. Single dose PD by post-dose change from baseline in serum chemistries with particular attention to Se-Ca, phosphate, magnesium, and creatinine. Urinalysis will also be performed.

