##### 3.1.1 Numbers of Cohorts and Participants, and Treatment Allocation

Up to approximately 30 participants may be enrolled to the study intervention such that approximately 24 evaluable participants complete the study.

Additional participants and cohorts may be enrolled pending review of study data and recommendation by a Data Monitoring Board (DMB) and ratification by the Sponsor.

Participants will be enrolled into 1 of up to 6 planned single dose cohorts (designated as S1 through S6, respectively) in ascending fashion.

Each cohort will consist of 4 participants randomized to receive either EXT608 or placebo, whereby 3 will receive a single injection of EXT608 and 1 will receive matching placebo.

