#### **3.3.4 Stratification, randomization and adaptive treatment allocation based on baseline covariates with strata**

In the modest planned cohort size, the DMB needs evaluable data up to and including Day 7 for a reliable dose escalation decision. Any participants for whom such data are not available will be replaced with a new participant receiving the same treatment assignment as the original participant to ensure the 3:1 ratio of active compound to control.

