#### **3.3.5 Blinding**

The primary outcome is safety and tolerability. The assessment relies partly on adverse events evaluations that are prone to reporting bias and can be effectively mitigated with the double-blind design.

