## 5.5 Treatment assignment, stratification, and randomization

Treatment allocation is performed in the EDC in a manner that ensures only the unblinded pharmacist or equivalent knows the treatment code.

The treatment assignment is computer generated by the EDC at the point of randomization. Participants are randomized 3:1 active:control in blocks of 4.

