### 8.3 Data Analysis

AEs will be presented in listings and Treatment Emergent Adverse Events (TEAEs) will be summarized. Individual results of laboratory tests (hematology, chemistry, and urinalysis) will be listed and change from baseline will be summarized using shift tables. Individual results of vital signs will be listed and observed values and changes from baseline will be summarized.

Individual results of quantitative ECG parameters from the 12-lead safety ECGs will be listed and observed values and changes from baseline will be summarized and analyzed consistent with the ICH E14 (3).

All summaries will be performed by placebo and each EXT608 dose level. Placebo data will be pooled across cohorts. Physical exam findings will be presented in data listings.

Concentrations of EXT608 will be summarized by dose over each scheduled sampling time using descriptive statistics. Individual plasma concentration data versus time will be presented in a data listing. PK parameters will be summarized by dose using descriptive

statistics. Dose proportionality will be assessed graphically and using a power model. PD will be presented in listings and summarized by dose and time point.

Detection of ADA and NAbs will be presented in listings and summarized by dose and time point.

No formal hypothesis testing will be conducted as part of this study.

DMB data packages will be based on the FAS for safety and PP for PK/PD.

Further details are described in the Statistical Analysis Plan.

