### **10.2 Data Management**

Data will be entered in the electronic data capture (EDC) system at the investigational site.

The data management plan will describe the methods used to collect, check, validate, and process clinical data in detail. It will also clarify the roles and responsibilities for the different functions and personnel involved in the data management process.

AEs and medical/surgical history will be classified according to the terminology of the Medical Dictionary for Regulatory Activities (MedDRA; version specified in the Data Management Plan). Medications will be classified according to the latest World Health Organization (WHO) Drug Dictionary.

Quality control procedures will be applied to each stage of data handling to ensure that all data are reliable and have been processed correctly. When all data have been coded, validated, and locked, clean file will be declared. Any treatment-revealing data may thereafter be added and the final database will be locked.

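### Protocol 5.4.2 leaves EXT608 concentrations unblinded, and no other section expressly keeps them from the people who rate adverse events

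*Protocol*

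**What the plan says.** **The open rule.** Protocol 5.4.2 consists of one sentence: "For safety reasons, no outcomes are blinded". EXT608 concentration is an outcome. The first secondary objective in 2.2 opens with "Single dose PK including" and goes on to list the exposure and elimination parameters.

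**The reason for blinding.** Protocol 3.3.5 says of the safety assessment: "The assessment relies partly on adverse events evaluations that are prone to reporting bias and can be effectively mitigated with the double-blind design".

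**Allocation.** Section 5.5: "Participants are randomized 3:1 active:control in blocks of 4". Section 3.1.1 describes cohorts of four, "whereby 3 will receive a single injection of EXT608 and 1 will receive matching placebo". Under 3.3.4, a participant without usable Day 7 data is "replaced with a new participant receiving the same treatment assignment as the original participant".

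**Where PK goes.** Section 6.9.4 has samples shipped in batches and gives no date, turnaround or recipient for results. Section 8.3: "DMB data packages will be based on the FAS for safety and PP for PK/PD". Section 7.3.2 times the cohort summary after the last participant's Day 7. Section 7.3.1 makes the Medical Monitor and the Investigator(s) voting DMB members.

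**Text that points towards blinding.** Section 5.4.1 keeps parties other than DMB members blind to treatment results until the DMB's reviews. Section 5.5 limits the code to the unblinded pharmacist or equivalent. Section 10.2 says, after declaration of clean file: "Any treatment-revealing data may thereafter be added and the final database will be locked". SAP 3.5 calls the interim summaries blinded.

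**The concern.** The safety reason given in 5.4.2 fits serum calcium and the safety laboratories. It does not explain opening drug concentrations: the decision tree in 3.1.5 uses CTCAE grade, suspected relatedness and serum calcium, and never PK. A measurable concentration is in effect the treatment code.

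AE severity and causality are ratings (6.10.1.1). They form the first primary measure, with a time frame to Day 28 (2.1), and suspected relatedness is the operative term in the escalation rules. Section 3.3.5 relies on the double-blind design to control bias in these ratings. Someone who follows 5.4.2 literally could pass concentrations to a rater without deviating from the protocol. The rater would then know who had active drug while AEs were still being collected, and could know a replacement's code before that person is dosed.

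**Working it through.** **1. The plan's own count.** 6 cohorts × 4 = 24, which matches the approximately 24 evaluable participants in 3.1.1. That is 6 × 3 = 18 active and 6 × 1 = 6 placebo. No figure based on power exists to check; 8.1 says the size is not set for inference.

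**2. What one code reveals.** A cohort is one block of three actives and one placebo, so there are 4 possible orderings.
- Placebo identified: 1 ordering remains, so all four codes are known.
- One, two or three actives identified: 3, 2 or 1 orderings remain.

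**3. Whether a negative profile identifies the placebo.** Let q be the probability that an active profile is entirely below the lower limit of quantification (LLOQ). The documents give no value, so q is an assumption. I also assume no false positives, and that profiles fall below the LLOQ independently. If one negative profile is seen and the other three are not, P(placebo) = 0.25 / (0.25 + 0.75q). The chance that the cohort shows exactly one negative profile is (1 − q)³.

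| q | P(placebo given one negative) | P(exactly one negative in cohort) |
|---|---|---|
| 0 | 1.00 | 1.00 |
| 0.1 | 0.77 | 0.73 |
| 0.25 | 0.57 | 0.42 |
| 0.5 | 0.40 | 0.13 |
| 1 | 0.25 | 0 |

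If all four profiles are seen and exactly one is negative, that one is the placebo.

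**4. Measurability by dose.** The inputs are the 4 µg starting dose (3.1.2) and the default LLOQ of 200 pg/mL (SAP 3.3.3.2). Taking dose/(V/F) as an upper bound on concentration (a one-compartment simplification), an active profile stays below the LLOQ whenever V/F exceeds dose/LLOQ. That is 4,000,000 pg ÷ 200 pg/mL = 20,000 mL = 20 L. At 4 µg the bound is 800 pg/mL for V/F of 5 L, 200 for 20 L and 50 for 80 L. The documents give no human V/F. If every step were the maximum 3-fold, the threshold would rise to 60, 180, 540, 1,620 and 4,860 L in cohorts 2 to 6. The deduction is therefore uncertain in the first cohort and more secure later.

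**5. AE rating time left.** With the minimum 72-hour stagger (3.1.3), dosing falls on cohort days 0, 3, 6 and 6. The last participant's Day 7 is cohort day 6 + 7 = 13. I assume no lag before the DMB review.

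| Participant | Study day at review | Days left to Day 28 |
|---|---|---|
| 1 | 13 − 0 = 13 | 15 |
| 2 | 13 − 3 = 10 | 18 |
| 3 and 4 | 13 − 6 = 7 | 21 |

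**6. Whether another section closes the gap.** None does so expressly.
- 5.4.1 concerns treatment results. It exempts DMB members, and its protection of everyone else runs only until the DMB's reviews.
- 5.5 restricts the code and does not mention data that reveal it.
- 10.2 says that such data may be added late and does not forbid earlier release.
- SAP 3.5 calls the summaries blinded, which does not fit the DMB exemption in 5.4.1.
- 6.9.4 is silent on recipients.

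**The case against.** **Disclosure is not stated.** A reader might infer that PK results will unblind each cohort around Day 7. The documents do not support that. They say that local laboratory reports and urine results go to the site (6.1.2.2, 6.8.2.2) and say nothing comparable for PK. Sections 5.4.1, 5.5, 10.2 and SAP 3.5 lean towards blinding. Much of the visit detail in 7.2 is not shown, and the Safety Plan, which may set routing, is not among the documents. This stands: the defect is a permission without an express bar, not a documented release.

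**Escalation is less exposed than it seems.** The tree uses seven-day safety data and no PK. If PK arrives with the Day 7 package, the ratings behind that cohort's decision were mostly made before it. This also stands. The exposure is to later AEs, re-rating and replacements.

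**Antibodies.** A reader might extend the point to anti-drug and neutralizing antibodies. Section 6.9.3 lists them among the safety laboratory tests and provides for investigator review of reports, so masking them would contradict the plan as written. That extension is not made here.

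**The gain is unquantified.** Serum calcium stays open, and 8.1 says its effect can be judged reliably in a cohort of four. Serum PTH is a PD variable (SAP 3.3.3.5), and the documents do not say how far it would reveal treatment. This stands in part. However, the first escalation rule provides for doses with no calcium effect. At such doses calcium says little about allocation, while a measurable concentration would reveal it.

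**Conclusion.** The concern holds as a gap and an inconsistency. Section 5.4.2 opens every outcome, PK is an outcome, and no section expressly withholds individual concentrations from AE raters, on whose blinding 3.3.5 depends. The clearest route is the DMB package, because 7.3.1 seats the Investigator(s) and Medical Monitor on the board and 5.4.1 exempts its members from the blind.

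If PK is seen at the earliest review, up to 4 of 4 codes in a cohort become known, with 15 to 21 days of AE rating left. Two readings go too far: that 21 days applies to everyone, and that one negative profile always identifies the placebo. The first is true only of the last two participants under the stagger. The second requires every active profile to be measurable, which is not assured at 4 µg with a 200 pg/mL LLOQ.

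The size rests on the minimum stagger, no review lag, PK being available by then, and no false positives. It should be corrected. It affects no sample size or error rate.

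**What to change.** Replace the sentence in 5.4.2 with text to this effect: *Serum calcium and safety laboratory results are open. Individual EXT608 concentrations are withheld from the Investigator, the Medical Monitor, other AE raters and blinded sponsor staff until clean file.*

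For the DMB package, send individual-level PK only to members who do not rate AEs, for example the independent statistician and the independent Safety Monitor. Other members see PK summaries that do not identify individuals. They lose nothing needed to apply the decision tree, which does not use PK. Simply routing PK to the DMB would not be enough, because the raters sit on it.

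Reconcile the related text:
- 5.4.1: narrow the DMB exemption accordingly, and say what happens to the blind after a review.
- 6.9.4: name the recipients and release date of PK results.
- 10.2: state that individual PK is treatment-revealing data.
- SAP 3.5: say which members receive blinded summaries.

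Leave antibody results as they are, or amend 6.9.3 at the same time if they are also to be withheld. The cost is wording and a data-transfer restriction. Sample size, dosing and emergency code-breaking (5.4.3) do not change.

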### 5.4.3 Breaking the blind

In case of a medical emergency for a participant, the Investigator and Medical Monitor have the capability to obtain the treatment code from the EDC. The reason for this action must be documented in the EDC.

## 5.5 Treatment assignment, stratification, and randomization

Treatment allocation is performed in the EDC in a manner that ensures only the unblinded pharmacist or equivalent knows the treatment code.

The treatment assignment is computer generated by the EDC at the point of randomization. Participants are randomized 3:1 active:control in blocks of 4.

## 5.6 Supply, storage and accountability

### 5.6.1 Test and Control Treatment and Labeling

Extend Biosciences, Inc. will supply test and control product. The products will be supplied bulk in 2 ml vials each labeled individually with a label that includes:

1. Product identity
2. Lot no. and manufacturing date
3. Recommended storage (protect from light)
4. The text: "Caution – for Investigational Use Only."
5. Manufacturer and address.

Storage for both is frozen at -20°C or less.

The products will be logged by the site pharmacy or equivalent, and accounting of all dispensed product will be performed.

### 5.6.2 Study Product Preparation

Study product is thawed in a room temperature water bath and has to be administered within 4 hours of thawing.

### **5.6.3 Concomitant medications**

No concomitant medications are supplied.

### **5.6.4 Ancillary supplies**

Not applicable.

## **5.7 Participant Compliance**

Participant compliance will be assessed by planned versus delivered medication, and completeness of data acquisition.

# **6 Procedures and Assessments Description**

This section describes how to collect and transfer the individual data to the Sponsor/CRO. The tables in [Section 7.1](#) describe what data has to be collected when, and [Section 7.2](#) outlines the activities in a logical but not mandatory sequence for ease of execution.

## **6.1 Collection Methodology and Data Flow**

### **6.1.1 Case Report Form (CRF)**

An electronic CRF (eCRF) will be supplied to the investigational site for collection of information. The eCRF is not considered source information and the investigational site must have the information available in source documentation.

### **6.1.2 Electronically uploaded data**

#### **6.1.2.1 Participant Files and Documents**

Participant files are uploaded in the EDC under the specific participant ID. These files may include:

1. photographs of the injection sites or
2. lesion from other AEs, or
3. files from other data collection devices, or
4. requested copies of source documents for remote source document verification (SDV)

#### **6.1.2.2 Laboratory Data**

Data from the local laboratory will be uploaded to the Sponsor/CRO directly. A test report will be sent to the site for inclusion in the participant chart; this will be considered source data.

## **6.2 Demographic Variables**

Demographic variables including the medical history and current medications will be obtained at the screening visit. All demographic data are entered into the EDC.

The data to be collected include:

### **6.2.1 Participant identification**

Participant sex, month and year of birth, and ethnic origin with the categories Caucasian, African-American, Hispanic, Asian and “other” with a text input field.

### **6.2.2 Medical History**

A medical history will be taken at screening. While serious conditions in the past have to be recorded, the emphasis will be on conditions within the last two years including completeness of currently ongoing conditions.

The medical history will include: disorders of head, eyes, ears, nose and throat; neoplastic and hematological disorders; infectious diseases; disorders of the cardiovascular system including hypertension and hyperlipidemia, each with duration; disorders of the respiratory system; disorders of the kidney and urinary tract; disorders of the gastrointestinal system; disorders of the immune system, connective tissue and joints; endocrinology and metabolism with a subcategory for diabetes including year of diagnosis, treatment, complications including nephropathy, neuropathy, and retinopathy; neurological disorders; and finally alcohol, illicit drug and smoking history including duration in years and number of pack years.

### **6.2.3 Concomitant medication**

A complete listing of current medications within the last three months including vitamins, herbal and dietary supplements with dose and frequency will be obtained at screening. Any medications taken throughout the study must be recorded in the eCRF. Acetaminophen may be given at the discretion of the Investigator.

## **6.3 Physical Exam**

### **6.3.1 Complete Physical Exam**

A complete physical exam will be performed at the screening and the last visit either when the participant has completed the full study or at an early termination. The physical exam will include: general appearance; head, eyes, ears, nose, throat, chest, lungs, heart, abdomen, musculoskeletal, skin neurological including reflexes. At the screening exam, any abnormalities found will be recorded in the eCRF under the medical history in the appropriate category. Any new findings at the last visit will be captured as an adverse event on the CRF for adverse events. The eCRF will thus not include any specific pages for physical exam.

### **6.3.2 Directed Physical Exam**

A directed physical exam based on reported symptoms will be conducted at the scheduled time points except for the first and last visit with the complete physical exam described above. Any new findings at the last visit will be captured as an adverse event on the CRF for adverse events.

## **6.4 Injection Site Assessment**

The intended injection site in the abdomen will be photographed prior to injection.

The injection site assessment includes evaluation of erythema, edema and any tenderness. The size of any erythema is measured with shortest and longest size in mm, and edema similarly in size and in addition the tallest height above surrounding skin. The measurement data are recorded in the EDC.

Any positive finding will be photographed with clear labeling next to the lesion of participant ID, date and time.

Following a positive finding the injection site will be photographed daily in the inpatient period, and subsequently at the clinics visits until resolved.

Minimally, the photographs

1. prior to injection,
2. when the event is at highest intensity, and
3. when resolved or stabilized

will be uploaded in the EDC.

A Visual Analog Scale (VAS) will be used for evaluation of injection site pain. A copy of the VAS is in [Appendix 2](#).

Positive events will furthermore be recorded as AEs.

## **6.5 Vital Signs: Pulse, Blood Pressure, Respiratory Rate and Temperature**

Pulse, diastolic and systolic blood pressure are measured sitting after five minutes rest. Automated instruments may be used.

Respiratory rate will be measured over at least 30 seconds if regular, if irregular, at least 1 minute.

Temperature will be measured orally.

These data are recorded in the EDC.

